## **Screening (Screening to Randomization)**

In case of a global health disruptive event, such as pandemic/epidemic (e.g. COVID-19), affecting the ability of the participant or the site to adhere to protocol requirements and assessments, investigators should only randomize participants if they expect them to be able to adhere to assessments and protocol-related activities. Evaluation of the eligibility of the participant should consider the ability to attend study visits and adhere to protocol assessments. If the latter is not anticipated, screening and randomization should not proceed, and re-screening (as allowable per protocol) should be considered when conditions allow for proper trial management.

## **During Treatment Period (Baseline to EOT)**

In case of a global health disruptive event, such as pandemic/epidemic (e.g. COVID-19), affecting the ability of the participant or the site to adhere to protocol requirements and assessments and therefore leading to a potential increase in the number of missing measurements, the Sponsor may consider recruiting additional participants to restore the sample size only after consultation with local regulatory authority.

## **Risks and Benefits**

Active infection should be excluded in order to comply with eligibility criteria (see [Section 5.2](#)).

The potential of secukinumab to increase the risk of infections has been identified (see IB Section 7.1). COVID-19 has similar impact on risk-benefit as other infections. No additional risk is anticipated due to COVID-19 infection.

## **Visits**

If the COVID-19 pandemic or similar situations that limits or prevents on-site study visits, alternative methods of providing continuing care may be implemented only for the visits outlined in the table above. Phone calls, virtual contacts (e.g. teleconsult) or visits by site staff to the participant's home depending on local regulations and capabilities, can replace on-site study visits, for the duration of the pandemic until it is safe for the participant to visit the site again. Any safety or efficacy assessments, which could not be feasible to perform or evaluate conduct remotely or virtually, the protocol deviation need to be recorded. Such data will be treated as missing data.

This **will not** apply to Screening, BSL, all clinic visits up to including Week 16, Week 24, Week 52 and Week 60 visit. For remaining visits per protocol, the above exceptions may be implemented, however, every effort need to be made to ensure on-site visit. If on-site visit is prevented at Screening or Baseline visit, the participants should not be randomized.

## **Laboratory assessments**

If the designated central laboratory is unable to operate, collection of samples may be modified by Novartis and if modified, will be communicated to the investigator. In such cases, it is acceptable to collect and perform laboratory tests at local laboratories that are certified for these

diagnostics. Similarly, sites should inform to the Sponsor of proposed changes to sample management/collection.

### **IMP (administration and dispensation)**

In case of a major health care event (e.g., COVID-19 pandemic, epidemic) that limits or prevents on-site study visits, delivery of IMP directly to a participant's home is generally permitted (if allowed by local regulations) in the event the Investigator has decided that an on-site visit by the participant is no longer appropriate or possible, and that it is in the interest of the participant's health to administer the study treatment even without performing an on-site visit. For changes in the distribution of trial drugs, the primary goal is to provide IMP to participants based on protocol to ensure participant safety and the integrity of clinical trials. Implementation will need to be discussed with Novartis. The dispatch of IMP from the site to the participant's home remains under the accountability of the Investigator. Each shipment/provisioning will be for a maximum of 1-month supply. In this case, regular phone calls or virtual contacts (every 4 weeks or more frequently if needed) will occur between the site and the participant for instructional purposes, safety monitoring, and discussion of the participant's health status until the participants can again visit the site.

IMP home administration is allowed only for the scheduled dosing visits (outlined in [Table 8-1](#)) if the participant or caregiver is trained on subcutaneous self-administration.

Changes in transportation and storage arrangements will not violate the blind design of treatment. The investigator should make relevant records such as the inventory and storage conditions of trial drugs.

### **Efficacy and Clinical Outcomes Assessments (COAs)**

In the event of a pandemic/epidemic that limits or prevents on-site study visits, selected efficacy assessments including Patient Reported Outcomes (PROs) can alternatively be done via web-based backup portal or visits of site staff to the participant's home, depending on local regulations and capabilities, and following any applicable training in the required process.

Exceptionally, if the electronic device is not working, the efficacy assessments and Patient Reported Outcomes may be completed using web-based backup portal for PROs. The data would then be transcribed in the vendor database.

For individual cases where the efficacy endpoint is not collected, the reasons for not obtaining the efficacy evaluation should be documented.

### **Imaging**

During the COVID-19 pandemic that limits or prevents on-site study visits, the collection of images may be modified by Novartis and will be communicated to the investigator.

## **Safety**

During the COVID-19 pandemic that limits or prevents on-site study visits, regular phone or virtual calls will occur (every 4 weeks or more frequently if needed) for safety monitoring and discussion of the participant's health status until the participant can again visit the site.

Female participants would be advised to perform the urine pregnancy test at home and report the result to the site. It is important that participants are instructed to perform the urine pregnancy test first and only if the test result is negative proceed with the administration of the study treatment.

## **Informed Consent Procedures**

During the COVID-19 pandemic that may challenge the ability to obtain a standard written informed consent due to limits that prevent an on-site visit, the Investigator may conduct the informed consent discussion remotely (e.g. telephone, videoconference). Guidance issued by local regulatory bodies on this aspect prevail and must be implemented and appropriately documented (e.g. the presence of an impartial witness, sign/dating separate ICFs by trial participant and person obtaining informed consent, etc.). Remote informed consent should be appropriately documented and confirmed by way of standard informed consent procedures at the earliest opportunity when the participant will be back at the trial sites.

## **Site monitoring**

In the event of a major health care disruption (e.g. pandemic, epidemic), requiring social distancing or limited travel/attendance to the clinical trial site, remote site initiation and monitoring could be considered.

**Note:** The details on operationalizing above-mentioned study management aspects during potential future pandemic/epidemic will be supplemented by study specific guidance to the clinical trial sites.

Clinical Development

CAIN457/Secukinumab/Cosentyx®

CAIN457I2301 / NCT04732117

A randomized, double-blind, placebo controlled, multicenter, phase III study of subcutaneous secukinumab to compare efficacy at 16 weeks with placebo and to assess safety and tolerability up to 52 weeks in Chinese participants with active non-radiographic axial spondyloarthritis

Statistical Analysis Plan (SAP) Amendment 2

Document type: SAP Documentation

Document status: Final

Release date: 8-Jan-2025

Number of pages: 56

Property of Novartis

For business use only

May not be used, divulged, published or otherwise disclosed

without the consent of Novartis

Template Version 3.0, Effective from 01-Jul-2020

Document History – Changes compared to previous final version of SAP

| Date | Time point | Reason for update | Outcome for update | Section and title impacted (Current) |
|---------------------------|----------------------|-------------------|---|---|
| 30 th Jan 2024 | Prior to DBL | Amendment 1 | Added age group for demographic summary table Added smoking status in summary table | 2.1 Data analysis general information |
| | Prior to DBL | Amendment 1 | Revised the baseline value definition | 2.1.1.3 Screening, baseline and post-baseline definitions |
| | Prior to DBL | Amendment 1 | Clarified the subgroup of interest | 2.2.1 Subgroup of interest |
| | Prior to DBL | Amendment 1 | Moved the original sensitivity analyses to supportive analyses. Removed non-parametric regression for ASAS40 | 2.5.4 Supportive analyses |
| | Prior to DBL | Amendment 1 | Clarified of the analyses of SF-36 PCS | 2.6.2 Statistical hypothesis, model, and method of analysis |
| | Prior to DBL | Amendment 1 | Corrected the CTCAE version from 4.0 to 4.03 | 2.7.3 Laboratory data |
| 8 th Jan 2025 | Prior to DBL | Amendment 1 | Change the definition of ASAS20 in case baseline evaluation equal to 0 and the percentage of worsening does not exist | 5.1 Description of efficacy variables |
| | Prior to DBL | Amendment 1 | Corrected the Newcombe Confidence interval expression | 5.5.2.1 Crude incidence and 100*(1- α)% confidence interval |
| | Prior to Week 52 DBL | Amendment 2 | Clarified the analyses window of Week 60 visit | 2.4.1.1 Visit window |
| | Prior to Week 52 DBL | Amendment 2 | Added the rule for post-baseline safety by-visit summary when there are multiple assessments with the same time of completion | 2.4.1.2 Multiple assessments within visit windows |

| | Secondary analysis..... | 50 |
| 5.5.2 | Crude incidence and related risk estimates | 52 |
| 5.5.3 | Exposure adjusted incidence rate and related risk estimates..... | 54 |
| 6 | References..... | 54 |

List of abbreviations

| | |
|-------------|---|
| ACR | American College of Rheumatology |
| AE | Adverse Event |
| ALT | Alanine Aminotransferase / Glutamic Pyruvic Transaminase / GPT |
| AS | Ankylosing Spondylitis |
| ASAS | Assessment of Spondyloarthritis International Society criteria |
| ASDAS | Ankylosing Spondylitis Disease Activity Score |
| AST | Aspartate Aminotransferase / Glutamic Oxaloacetic Transaminase / GOT |
| ASQoL | Ankylosing Spondylitis Quality of Life Questionnaire |
| BASDAI | Bath Ankylosing Spondylitis Disease Activity Index |
| BASFI | Bath Ankylosing Spondylitis Functional Index |
| ████████ | ████████ |
| BSL | Baseline |
| cDMARD | conventional (i.e., non-biologic) DMARD |
| CPO | Country Pharma Organization |
| CRF | Case Report Form |
| CRP (hsCRP) | (high sensitivity) C-Reactive Protein |
| CRP+ | hsCRP > ULN (as defined by the central lab) |
| CSR | Clinical Study Report |
| DMARD | Disease Modifying Antirheumatic Drug |
| DMC | Data Monitoring Committee |
| DMS | Document Management System |
| ECG | Electrocardiogram |
| eCRF | electronic Case Report/Record Form |
| EMA / EMEA | European Medicines (Evaluation) Agency |
| ████████ | ████████ |
| FAS | Full Analysis Set |
| GCP | Good Clinical Practice |
| GGT | Gamma Glutamyl Transferase |
| HLA | Human Leukocyte Antigen |
| IA | Interim Analyses |
| ICH | International Conference on Harmonization of Technical Requirements for Registration of Pharmaceuticals for Human Use |
| IEC | Independent Ethics Committee |
| IL | Interleukin |
| IRB | Institutional Review Board |
| IRT | Interactive Response Technology |
| MAR | Missing At Random |
| ████████ | ████████ |
| MCS | Mental Component Summary |
| MedDRA | Medical Dictionary for Drug Regulatory Affairs |
| MI | Multiple Imputation |
| MMRM | Mixed Model Repeated Measures |
| MNAR | MRI |
| MRI | Magnetic Resonance Imaging |
| MRI+ | Positive for sacroiliitis (active inflammatory lesions) |

| | |
|----------|---|
| MTX | Methotrexate |
| nr-axSpA | Non-radiographic axial SpondyloArthritis |
| NRI | Non-Responder Imputation |
| NSAID | Non-Steroidal Anti-Inflammatory Drug |
| PCS | Physical Component Summary |
| PD | Pharmacodynamic |
| PG | Pharmacogenetic |
| PK | Pharmacokinetics |
| PoC | Proof of Concept |
| PRN | According to need, as required |
| PPS | Per-Protocol Set |
| PRO | Patient-reported Outcomes |
| PsA | Psoriatic Arthritis |
| QoL | Quality of Life |
| RA | Rheumatoid Arthritis |
| RAP | Reporting & Analysis Process |
| SAE | Serious Adverse Event |
| SAP | Statistical Analysis Plan |
| SAS | Statistical Analysis System |
| s.c. | Subcutaneous(ly) |
| SCR | Screening |
| SF-36 | Medical Outcome Short Form (36) Health Survey |
| SpA | Spondyloarthritis |
| TFLs | Tables, Figures, Listings |
| TNF | Tumor Necrosis Factor |
| TNF-IR | TNF α Inhibitor Incomplete Responders |
| ULN | Upper Limit of Normal |
| VAS | Visual Analog Scale |
| WHO | World Health Organization |

1 Introduction

Data will be analyzed by Novartis according to this SAP and the data analysis Section 12 of the clinical study protocol. The statistical methodology is described below and any deviations from the protocol are documented. Additional detailed information regarding the analysis methodology is contained in the Appendix section.

1.1 Study design

This is a randomized, double-blind, placebo-controlled study of secukinumab 150 mg s.c. to evaluate the safety, tolerability, and efficacy in Chinese participants with active non-radiographic axial spondyloarthritis (nr-axSpA).

A screening period of up to 10 weeks before randomization will assess participant eligibility, followed by 16 weeks of double-blind treatment period and 44 weeks open label period.

Approximately 134 participants will be randomized in a ratio of 1:1 to receive secukinumab 150 mg s.c. or placebo:

- Group 1: secukinumab 150 mg (1mL, 150 mg/mL) s.c. pre-filled syringe (PFS) at baseline (BSL), Weeks 1, 2, and 3, followed by administration every four weeks starting at Week 4
- Group 2: placebo (1 mL) s.c. PFS at BSL, Week 1, 2 and 3, followed by administration every four weeks starting at Week 4

Participants will be stratified at randomization according to the subgroup of objective sign of inflammation they belong to (based on their CRP and MRI status at screening: CRP+ and MRI+, CRP+ and MRI-, CRP- and MRI+).

Additionally, it is planned to enroll no more than approximately 10% Tumor Necrosis Factor – Inadequate Response (TNF α -IR) participants in the study.

The primary analysis will be performed after all participants complete Week 16 visit to support registration in China.

From Week 16, all participants will switch to open label secukinumab 150 mg s.c., including all placebo participants. The first dose of open label secukinumab 150 mg s.c. should start at the Week 16 visit, only after performing all assessments for that visit. However, all participants and investigators/site staff will remain blinded to the original randomized treatment group assignment (150 mg vs placebo).

At Week 24, non-responders (defined as not achieving ASAS20) will be escalated to secukinumab 300 mg s.c. Responders will continue secukinumab 150 mg s.c. treatment.

Study treatment will continue up to Week 48.

At end of treatment visit will be performed 4 weeks after last study treatment administration i.e. at Week 52 and a post treatment follow-up visit is to be done 12 weeks after last study treatment administration for all participants (regardless of whether they complete the entire study as planned or exit the study early).

A primary endpoint analysis will be conducted after all participants complete Week 16 visit. The final analysis will be conducted on all participant data at the time the study ends.

[figure not shown]
Interim analysis is not applicable in this study.

[figure not shown]
1.2 Study objectives and endpoints

Table 1-1 Objectives and related endpoints

| Objective(s) | Endpoint(s) |
|--|---|
| Primary objective(s) | Endpoint(s) for primary objective(s) |
| 
To assess the efficacy of secukinumab 150 mg s.c. relative to placebo at Week 16 based on the proportion of TNF-α naive patients achieving an ASAS40 response (Assessment of SpondyloArthritis International Society criteria). | 
ASAS40 response rate at Week 16 ASAS40 response is defined as an improvement of $\geq 40\%$ and an absolute improvement from baseline of ≥ 2 units on a 10-point scale in at least three of the four main domains and no worsening assessed at all in the remaining domain. Main ASAS domains:
Patient's global assessment of disease activity measured on a VAS scalePatient's assessment of back pain, represented by either total or nocturnal pain scores, both measured on a VAS scaleFunction represented by BASFI average of 10 questions regarding ability to perform specific tasks as measured by VAS scaleInflammation represented by mean duration and severity of morning stiffness, represented by the average of the last 2 questions on the 6-question BASDAI as measured by VAS scale |
| Secondary objective(s) | Endpoint(s) for secondary objective(s) |
| 
To assess the efficacy of secukinumab 150 mg s.c. relative to placebo at Week 16 based on the proportion of overall patients achieving an ASAS40 response.To assess the efficacy of secukinumab 150 mg s.c. relative to placebo at Week 16 based on the proportion of patients meeting the ASAS 5/6 response criteria.To assess the efficacy of secukinumab 150 mg s.c. relative to placebo at Week 16 based on the change from baseline in total Bath Ankylosing Spondylitis Disease Activity Index (BASDAI).To assess the efficacy of secukinumab 150 mg s.c. relative to placebo at Week 16 based on the proportion of patients achieving BASDAI 50. | 
ASAS40 response rate in overall patients at Week 16ASAS 5/6 response rate at Week 16 ASAS 5/6 response is defined as an improvement of $\geq 20\%$ in at least five of all six domains.Change from baseline in total BASDAI at Week 16BASDAI 50 proportion at Week 16 BASDAI 50 is defined as an improvement of at least 50% in the BASDAI total score compared to baseline. |

| Objective(s) | Endpoint(s) |
|---|---|
| 
 To assess the efficacy of secukinumab 150 mg s.c. relative to placebo at Week 16 based on the change from baseline of high sensitivity C-Reactive Protein (hsCRP). | 
 Change from baseline in hsCRP at Week 16 |
| 
 To assess the efficacy of secukinumab 150 mg s.c. relative to placebo at Week 16 based on the change from baseline in total Bath Ankylosing Spondylitis Functional Index (BASFI). | 
 Change from baseline in BASFI at Week 16 |
| 
 To assess the efficacy of secukinumab 150 mg s.c. relative to placebo at Week 16 based on the change from baseline in sacroiliac (SI) joint edema on MRI. | 
 Change from baseline in SI joint edema score on MRI at Week 16 |
| 
 To assess the efficacy of secukinumab 150 mg s.c. relative to placebo at Week 16 based on the proportion of subjects achieving an ASAS20 response. | 
 ASAS20 response rate at Week 16 ASAS20 response is defined as an improvement of $\geq 20\%$ and an absolute improvement from baseline of ≥ 1 unit on a 10-point scale in at least three of the four main domains and no worsening of $\geq 20\%$ and ≥ 1 unit at all in the remaining domain. |
| 
 To assess the efficacy of secukinumab 150 mg s.c. relative to placebo at Week 16 based on the change from baseline in Short Form-36 Physical Component Summary (SF-36 PCS). | 
 Change from baseline in SF-36 PCS at Week 16 |
| 
 To assess the efficacy of secukinumab 150 mg s.c. relative to placebo at Week 16 based on the change from baseline in Ankylosing Spondylitis Quality of Life (ASQoL) scores. | 
 Change from baseline in ASQoL score at Week 16 |
| 
 To assess the efficacy of secukinumab 150 mg s.c. relative to placebo at Week 16 based on the proportion of patients achieving ASAS partial remission. | 
 ASAS partial remission rate at Week 16 ASAS partial remission is defined as a value not above 2 units in each of the four main ASAS domains on a 10-point scale. |
| 
 To evaluate overall safety and tolerability of secukinumab. | 
 Number of participants with adverse events (AE) serious adverse events (SAE), clinically significant changes in laboratory value and vital signs. |

2 Statistical methods

2.1 Data analysis general information

The primary endpoint analysis will be performed after all participants complete Week 16 or discontinued earlier and the final analysis will be conducted on all participant data at the time the study ends, both by Novartis. Any data analysis carried out independently by the investigator should be submitted to Novartis before publication or presentation.

Novartis will perform the analysis at Week 16 and final analysis. Statistical software SAS version 9.4 or later will be used.

Summary statistics for continuous variables will generally include the number of participants (N), minimum, lower quartile, mean, standard deviation (SD), median, upper quartile, and maximum. For binary or discrete variables, the absolute number of participants in each category and relative frequencies will be provided.

Unless otherwise specified, two-sided 95% confidence intervals will be displayed.

In case of a global health disruptive event, such as pandemic/epidemic (e.g., COVID-19), affecting the ability of the patient or the site to adhere to protocol requirements and assessments and therefore leading to a potential increase in the number of missing measurements, additional analysis populations may be defined as per the instructions and procedures outlined in Section 16.9 in the protocol.

The efficacy evaluation of secukinumab relative to placebo will generally focus on the first 16 weeks of treatment unless otherwise specified.

Data analysis will be presented by treatment group. Efficacy and safety data for the 16-week placebo-controlled period and the entire treatment period as appropriate will be presented by the following two treatment groups. Participants may be included in more than one treatment group for some analysis (e.g. exposure adjusted adverse events over the entire treatment period).

These treatment groups represent the regimens to which participants will be eligible to be randomized:

- Secukinumab 150 mg regimen
- Placebo regimen

Note that the treatment groups above for a participant may differ depending on the time period of the analysis and whether one assesses the participant for efficacy or safety.

Data may also be presented after Week 16, by a combination of the ‘original’ and ‘switch’ treatment groups. These treatment groups represent the treatment combinations the participants experience over the course of the entire trial. (e.g., placebo participants who are reassigned to secukinumab 150 mg, non-responders who are escalated to secukinumab 300 mg).

All listings will be presented by treatment sequence.

2.1.1 General definitions

2.1.1.1 Treatment groups

The summaries by treatment will be performed by the randomized treatment or treatment sequence.

- Randomized treatment:
 - AIN457 150 mg s.c.
 - Placebo s.c.
- Treatment sequence:
 - AIN457 150 mg
 - AIN457 150 mg – AIN457 300 mg
 - Placebo
 - Placebo – AIN457 150 mg
 - Placebo – AIN457 150 mg – AIN457 300 mg

For some safety summaries (e.g. exposure-adjusted) the ‘switch’ treatment may be summarized separately:

Week 1 – Week 16: AIN457 150 mg, Placebo

Entire study: Any AIN457 150 mg, Any AIN457 300 mg, Any AIN457, Placebo

Unless otherwise specified, at the primary endpoint analysis, efficacy data for the placebo-controlled period and safety data up to Week 16 and Entire study will be presented. Additional aspects of efficacy, safety and tolerability of secukinumab will be investigated in the final analysis. Additional analyses may also be performed to support interactions with health authorities, as necessary.

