## 1.2 Purpose

The purpose of this bridging study is to evaluate efficacy, safety and tolerability of secukinumab 150 mg s.c. compared to placebo in Chinese participants with active nr-axSpA at Week 16 to support registration in China. Meanwhile, this study will also observe the long-term efficacy, safety and tolerability of secukinumab including spinal and SI-joint inflammation as evidenced by magnetic resonance imaging (MRI) at Week 52.

Additionally, efficacy, safety and tolerability of secukinumab 300 mg s.c. will be assessed in non-responders, defined as participants who have not achieved ASAS20 at Week 24.

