2.4 Treatments (study treatment, rescue medication, concomitant therapies, compliance)

2.4.1 Study treatment / compliance

The analysis of study treatment data will be based on the safety set. The number of active and placebo injections will be presented by treatment group.

The duration of exposure to study treatment will also be summarized by treatment group. In addition, the number and percentage of participants with cumulative exposure levels (e.g. any exposure, ≥ 1 week, ≥ 2 weeks ≥ 3 weeks, ≥ 4 weeks, ≥ 8 weeks, etc.) will be presented.

Duration of exposure is defined as the time from first dose of study treatment to the time of treatment switch (for participants who switch treatment) or minimum of (last dose of the treatment + 84 days) and (last visit date). Participants who switch treatment during the study (e.g. from placebo to active treatment) will have exposure to both medications using the appropriate start and stop dates.

Duration of exposure (years) = duration of exposure (days) / 365.25

Duration of exposure (100 subject years) = duration of exposure (years) / 100

The analysis of duration of exposure described above will be done for the entire study treatment period.

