Table 2-3 Overview of analysis on some safety endpoints

| Analysis period | AEs & SAEs | AEs-SMQ | AEs by severity | study drug related AEs | Notables for (vitals/ECG), lab criteria | Risk |
|------------------|--|-------------------------------|-------------------|------------------------|---|--|
| Day 1 – Week 16 | • crude incidence | • crude incidence | • crude incidence | • crude incidence | • crude incidence | • crude incidence |
| Entire Treatment | • crude incidence • exp.time adjusted incidence | • exp.time adjusted incidence | • crude incidence | • crude incidence | • crude incidence | • crude incidence • exp.time adjusted incidence |

* Exposure-adjusted incidence rates will be done for the following:

- At the PSOC for AE and SAE
- At the PT level for common AEs, which is defined as at least 2% of the patients in the secukinumab during the initial treatment period (i.e. up to week 16) or events that had an incidence rate of at least 5.0 cases per 100 subject-years in the combined secukinumab groups during the entire treatment period
- At Level 1 for Risks and SMQ analyses

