5.5.3 Exposure adjusted incidence rate and related risk estimates

5.5.3.1 Exposure adjusted incidence rate and 100*(1- α)% confidence interval

It will be assumed that for each of n subjects in a clinical trial the time t_j ($j = 1, \dots, n$) to the first occurrence of a certain event is observed, or if the event was not experienced, the (censored) time to the end of the observation period. The sequence of first occurrences of an event will be modeled to follow approximately a Poisson process with constant intensity θ . The rate parameter θ will be estimated as $\lambda = D/T$, where $T = \sum_{j=1}^n t_j$ and D is the number of subjects with at least one event. Conditionally on T , an exact $100*(1-\alpha)\%$ confidence interval for a Poisson variable with parameter θT and observed value D can be obtained based on (Garwood, 1936), from which an exact $100*(1-\alpha)\%$ confidence interval for D/T will be derived as follows (Sahai, 1993; Ulm, 1990):

$$\text{Lower confidence limit } L = \frac{0.5c_{\alpha/2,2D}}{T} \text{ for } D > 0, 0 \text{ otherwise,}$$

$$\text{Upper confidence limit } U = \frac{0.5c_{\alpha/2,2D+2}}{T}$$

Where $c_{\alpha,k}$ is the α th quantile of the Chi-square distribution with k degrees of freedom.

The example below shows how this should be handled for cases where subjects switch treatment. In particular for summarizing 'Any AIN' as a group, one should take into consideration the sequence of treatments while calculating exposure time for subjects.

Table 5-3 Examples for calculating exposure time for incidence rates (IR)

| 1st treatment | 1st exposure | 2nd treatment | 2nd exposure | Event days (in terms of study day) | Exposure for IR |
|---------------|--------------|---------------|--------------|--|---|
| Placebo | 100 days | 150 mg | 200 days | 50 (1st trt) 110 (10 days into 2nd trt) | Placebo: 50 days (event) 150 mg: 10 days (event) Any AIN: 10 days (event) |

6 References

Garwood, F. (1936) Fiducial limits for the Poisson distribution. *Biometrika*; 46: 441-453.

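### The entire-study safety columns for 150 mg and 300 mg cover different parts of treatment, and no committed table gives event rates for the two doses over the same weeks

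*SAP*

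**What the plan says.** Protocol 1.2 makes the higher dose a purpose of the study: "efficacy, safety and tolerability of secukinumab 300 mg s.c. will be assessed in non-responders". The route to it is fixed in SAP 1.1. First, "From Week 16, all participants will switch to open label secukinumab 150 mg s.c., including all placebo participants". Then, "At Week 24, non-responders (defined as not achieving ASAS20) will be escalated to secukinumab 300 mg s.c".

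On safety reporting:

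- **Columns.** SAP 2.1.1.1 groups summaries by randomized treatment or by treatment sequence. It adds that for some safety summaries, with exposure-adjusted ones as the example, the switch "treatment may be summarized separately". The whole-study version is "Entire study: Any AIN457 150 mg, Any AIN457 300 mg, Any AIN457, Placebo".
- **Exposure.** Under SAP 2.4.1, participants who switch "will have exposure to both medications using the appropriate start and stop dates".
- **Rate.** SAP 5.5.3.1 divides the number of participants with at least one event by the summed time to first event or censoring. First occurrences "will be modeled to follow approximately a Poisson process with constant intensity".
- **Periods.** The table headed "Table 2-3 Overview of analysis on some safety endpoints" has two rows, Day 1 to Week 16 and the entire treatment period. Exposure-adjusted rates appear only in the second.
- **Permission.** SAP 2.7 says safety may be given for each treatment period separately, as appropriate. Protocol 6.1.3 defines Treatment Period 3 as Week 24 onward, with responders staying on 150 mg and non-responders receiving 300 mg.

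**The concern.** Dividing by person-time corrects for how long each dose was given. It does not correct for which part of treatment that time comes from. The 150 mg column contains the start of secukinumab treatment for everyone: the weekly doses and the rest of the first 24 weeks in Group 1, and Weeks 16 to 24 in Group 2, which starts active drug on the four-weekly schedule. The 300 mg column contains nothing before Week 24. Anyone who stopped earlier for intolerance counts under 150 mg and can never count under 300 mg.

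A constant intensity would make this harmless. If the intensity declines with time on drug, the 150 mg rate is raised by early exposure and the 300 mg rate is not.

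At stake is the reading of the 300 mg safety data. Protocol 4.2 already calls the safety of the two doses comparable, citing studies in other indications. A ratio below 1 that comes only from timing could be taken as confirmation in this disease. The primary endpoint is not affected.

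**Working it through.** **The plan's own figure.** The plan gives no adverse event rate to reproduce. The nearest item is the example in SAP Table 5-3: 100 days on placebo, then 150 mg, with an event on study day 110. The 150 mg time is 110 − 100 = 10 days, as printed. This confirms that time is counted afresh from a switch.

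**Inputs from the documents.** 134 participants, 1:1, so 67 per arm; placebo to 150 mg at Week 16; escalation at Week 24; last dose Week 48; follow-up to last dose + 84 days, which is Week 60. Time after escalation is therefore 60 − 24 = 36 weeks.

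**Assumptions.** 35% escalated in each arm; no dropout; no dose effect; a rate in the first 16 weeks after the first active dose that is *k* times the later rate; total event rates; 52 weeks per year.

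**Exposure.**

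- 150 mg: 67×24 + 67×8 + 134×0.65×36 = 1608 + 536 + 3135.6 = 5279.6 weeks = 101.5 patient-years.
- 300 mg: 134×0.35×36 = 1688.4 weeks = 32.5 patient-years.

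**Share of each column within the first 16 active weeks.** Former placebo participants are still in this window from Week 24 to Week 32.

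- 150 mg: (67×16 + 67×8 + 67×0.65×8) / 5279.6 = (1072 + 536 + 348.4) / 5279.6 = 0.371.
- 300 mg: (67×0.35×8) / 1688.4 = 187.6 / 1688.4 = 0.111.

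**Rate ratio 300/150 with no dose effect** = [1 + 0.111(k − 1)] / [1 + 0.371(k − 1)].

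| k | Calculation | Ratio |
|---|---|---|
| 1 | 1 / 1 | 1.00 |
| 1.5 | 1.056 / 1.185 | 0.89 |
| 2 | 1.111 / 1.371 | 0.81 |
| 3 | 1.222 / 1.741 | 0.70 |

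**Range of escalation.** Letting each arm escalate between 25% and 45%, with k from 1.5 to 3, gives 0.66 to 0.91. The low end is 45% in Group 1, 25% in Group 2, k = 3: early shares 2010/5279.6 = 0.381 and 134/1688.4 = 0.079, so 1.159/1.761 = 0.66. The high end is 25% and 45%, k = 1.5: early shares 1902.8/5279.6 = 0.360 and 241.2/1688.4 = 0.143, so 1.071/1.180 = 0.91.

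**The SAP's first-event estimator.** Expected rates under SAP 5.5.3.1, with time restarted at the switch, 20% to 50% escalated and late rates of 20 to 150 per 100 patient-years (all assumed), give ratios of 0.82–0.89, 0.70–0.82 and 0.54–0.70 for k = 1.5, 2 and 3. With a constant hazard the ratio is 1.00.

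**Same weeks for both doses.** From Week 24, with 35% escalated in both arms, the early share is 348.4/3135.6 = 0.111 on 150 mg and 0.111 on 300 mg, so the ratio is 1.00 for every k.

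**Why the arms must be shown.** If 25% of Group 1 and 45% of Group 2 escalate, the pooled early shares from Week 24 are 294.8/3135.6 = 0.094 on 150 mg and 241.2/1688.4 = 0.143 on 300 mg. The pooled ratio is then 1.02 (k = 1.5) to 1.08 (k = 3). Within an arm the shares are equal (0 in Group 1, 8/36 in Group 2), and the ratio is again 1.00.

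**The case against.** The strongest reply is that the SAP does not plan a dose comparison. The dose columns are optional, SAP 2.7 rules out formal testing of safety, and the same section already permits summaries by treatment period, which would include the table wanted here. The default grouping by treatment sequence separates those who escalated from those who did not and keeps the original arm. Laboratory and ECG changes are summarized visit by visit; shown by sequence, they give same-week views after Week 24. Table 2-3 calls itself an overview of some endpoints, and redacted SAP sections may hold further 300 mg analyses.

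Most of this stands. It rules out saying that the SAP has chosen a misleading comparison, or that no same-week view of any kind is possible. It does not supply event rates. The sequence groups pool time before and after escalation, so they do not isolate 300 mg, and the permission in SAP 2.7 fixes neither the period, the columns nor the exposure start.

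The size can also be challenged. No document gives an event rate or a time pattern. If rates differ between people but are constant within each person, restarting the clock at the switch gives ratios slightly above 1 (1.01 to 1.08 in the cases tried). Selection of non-responders could push either way. Crude incidence has no fixed direction: with 50% escalated and a constant 100 events per 100 patient-years it is 44.1% on 150 mg and 49.8% on 300 mg. The mismatch is certain; its direction is conditional.

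**Conclusion.** The concern holds in a limited form. The entire-study 150 mg and 300 mg columns are not like for like, and the visible text commits to no table of event rates for the two doses over the same weeks, although 300 mg safety is a stated purpose.

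The size depends on a falling event rate, which is assumed. At 35% escalation the ratio is about 0.89, 0.81 or 0.70 for an early rate 1.5, 2 or 3 times the later one, 0.66 to 0.91 over 25% to 45% escalation by arm, and 1.00 if the rate is constant.

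A reader might infer three stronger things that the documents do not support:

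- **That 300 mg will look safer.** It can, under a declining rate; nothing in the documents establishes that pattern.
- **That the 150 mg column holds all early exposure, weekly active doses included, for everyone.** Weekly active doses are given in Group 1 only, and about 11% of 300 mg time falls within the first 16 active weeks of former placebo participants.
- **That the SAP intends to draw a dose conclusion from these columns.** They are optional and descriptive.

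**What to change.** Turn the permission in SAP 2.7 into a commitment. Add a third period, Week 24 to end (Treatment Period 3), to SAP 2.1.1.1 and Table 2-3 for adverse events, serious adverse events and risks. Use two columns, continued 150 mg and escalated to 300 mg, count exposure from the Week 24 dose, and show results by original arm and not only pooled.

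Add two footnotes: the groups are non-randomized, being responders against non-responders; and the entire-study any-150 mg and any-300 mg columns are not a dose comparison.

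The cost is one more run of existing tables. Exposure is smaller: at 35% escalation about 60.3 patient-years on 150 mg (3135.6/52) and 32.5 on 300 mg, about half of each per arm. The table removes the timing mismatch but not the difference between responders and non-responders, so it stays descriptive.
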